2.3.3 Data Included in the Extended Follow-up Phase

Patients whose peripheral B cells remain depleted at the common closeout date will enter the Extended Follow-up phase. For patients who enter this phase all of their screening data plus post Follow-up phase data will be included in this analysis.

[REDACTED]

[REDACTED]

[REDACTED]

3. STATISTICAL METHODS OVERVIEW

As this is an open-label, single-arm study, with primary objectives regarding safety and PK there will be no formal statistical hypothesis testing.

The day of enrollment (Day 1) will be considered the day the patient receives their first infusion, or part thereof, of rituximab.

For binary endpoints the number and percentage of patients will be presented by visit. At key time points (Month 6, 12 and 18) two-sided 95% Confidence intervals (CIs) for the percentage of patients will be calculated.

For continuous endpoints, the n, mean, median, standard deviation (SD), minimum and maximum values will be presented by visit with two-sided 95% CIs for the mean presented for the data at key time-points (Months 6, 12 and 18), unless stated otherwise.

When we have 0 counts, please don't display 0.0%

3.1 Analysis Populations

3.1.1 Safety Population

All patients who received at least part of one infusion of rituximab will be included in the safety population.

Safety and efficacy analyses will be based on the safety population.

3.2 Baseline Demographics and Baseline Information

Details of the analyses and outputs are given in Section 4.

3.2.1 Definition of Remission Induction Phase Baseline

Baseline will be defined as the last available pre-treatment value taken on or before the initiation of rituximab (RTX) treatment on study treatment Day 1, and will be used for summary of demographic characteristics, as well as for all change-from-baseline analyses of efficacy, safety, and PD endpoints.

Special rules apply for the determination of the PVDI baseline score to account for missing individual scores: see Section 10.

For endpoints that are defined in terms of change from baseline, patients who do not have a pre-treatment value reported for a particular assessment (if any) will be excluded from the change-from-baseline analyses for that assessment.

3.2.2 Follow-up Phase Baseline

The Follow-up phase will use the same baseline values as the Remission Induction phase for all analyses.

3.2.3 Extended Follow-up Phase Baseline

Baseline will be defined as the last available value taken on or before the start of the Extended Follow-up phase, and will be used for all change-from-baseline analyses of safety and PD

endpoints. For B cell depletion (absolute CD19 count) we should use the baseline value prior to receiving study medication.

For endpoints that are defined in terms of change from baseline, patients who do not have a pre-treatment value reported for a particular assessment (if any) will be excluded from the change-from-baseline analyses for that assessment.

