1. BACKGROUND

This document provides specifications for the primary analysis including, remission induction phase, follow-up phase and extended follow-up phase, of the study WA25615.

- **Remission Induction Phase:** Day 1 until end of month 6.
- **Follow-Up Phase:** Post month 6 until common closeout date, where common closeout date is 18 months after the enrolment of the last patient.
- **Extended Follow-Up Phase:** Post common closeout date until CD19 B-cell counts have returned to baseline level or within normal range, whichever is lower.

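### SAP 3.2.3 measures extended follow-up changes from a value normally taken after rituximab, so immunoglobulin changes in that phase omit any fall before closeout and cannot be compared with earlier phases

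*SAP*

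**What the plan says.** SAP 3.2.1 sets the induction baseline as the "last available pre-treatment value taken on or before the initiation of rituximab (RTX) treatment on study treatment Day 1". SAP 3.2.2 keeps it: "The Follow-up phase will use the same baseline values as the Remission Induction phase for all analyses".

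SAP 3.2.3 departs from this for extended follow-up, where baseline becomes: "last available value taken on or before the start of the Extended Follow-up phase, and will be used for all change-from-baseline analyses of safety". The scope is wide, since PD endpoints are covered too. There is one exception: "For B cell depletion (absolute CD19 count) we should use the baseline value prior to receiving study medication". The section ends with an exclusion rule: "patients who do not have a pre-treatment value reported for a particular assessment (if any) will be excluded from the change-from-baseline analyses" for that assessment.

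Four other places matter:

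- SAP 1 starts the phase after common closeout, "where common closeout date is 18 months after the enrolment of the last patient".
- SAP 2.3.3 admits patients who are still B-cell depleted at closeout. It builds the data set from screening data plus data collected after the follow-up phase.
- SAP 7.3 summarizes immunoglobulins by visit and study phase, both as levels and as changes from baseline.
- Protocol 3.1.4 keeps immunoglobulins under assessment during extended follow-up.

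**The concern.** The word baseline has one meaning up to closeout and another after it. For immunoglobulins, a patient whose IgG fell after rituximab and stayed down would show a change near zero in extended follow-up, and a partial recovery would read as a net gain. Neither number could be set beside the induction or follow-up changes, which are measured from before rituximab.

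This bears on a safety question that the documents themselves raise. Protocol 5.2.3.7 records hypogammaglobulinemia in children after rituximab, in some cases severe and prolonged. SAP 2.3 reports extended follow-up in a separate final analysis, so its change figures may be read apart from those of the earlier phases. The CD19 exception retains the pre-medication reference for depletion; no reason is given for treating immunoglobulins differently.

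**Working it through.** This is a matter of definition. The plan states no figure for it, so there is none to reproduce.

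**1. Where the new baseline falls.** Protocol Appendix 2 puts Month 18 at Day 545 ± 10. For a patient who completes follow-up, the phase-start value is therefore normally no earlier than 545 − 10 = Day 535, against Day 1 or before under SAP 3.2.1. Protocol 4.3.4 allows further rituximab courses after Month 6 until closeout, so the value may also follow retreatment. The rule could fall back to a pre-treatment value only if a test had no later result. That should be rare, because immunoglobulins are scheduled at every visit from Month 1.

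**2. What drops out.** Let Y0 be the last pre-rituximab value, Yc the phase-start value and Yt a later value.

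- Change under SAP 3.2.3: Yt − Yc
- Change from pre-treatment: Yt − Y0
- Difference: (Yt − Yc) − (Yt − Y0) = Y0 − Yc

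The difference is the fall accrued before the phase began. If Yc = Y0, the two measures agree.

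**3. Illustration for IgG.** The documents give no expected IgG fall, so these values are assumptions.

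| Case (Y0 = 10 g/L, 30% fall, Yc = 7.0) | Yt | Yt − Yc | Yt − Y0 |
|---|---|---|---|
| No recovery | 7.00 | 0.00 | −3.00 |
| A quarter of the fall recovered | 7.75 | +0.75 | −2.25 |

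Over Y0 of 8 to 12 g/L and falls of 10% to 50%, the omitted amount runs from 8 × 0.10 = 0.8 g/L to 12 × 0.50 = 6.0 g/L.

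**4. Consistency of the text.**

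- The exclusion sentence in SAP 3.2.3 repeats the one in 3.2.1. It fits there, because that baseline is pre-treatment. In 3.2.3 it would drop a patient who has a valid phase-start value but no pre-treatment one.
- SAP 2.3.2 assigns values dated on or before entry to extended follow-up to the follow-up data set. SAP 2.3.3 carries forward only screening data and adds data from after the follow-up phase. Read literally, the extended follow-up set lacks the phase-start value that 3.2.3 needs. It also lacks a Day 1 pre-dose value, which 3.2.1 would often select.

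**5. Which outputs are touched.** For immunoglobulins, the by-phase instruction in SAP 7.3 brings the rule into play. SAP 7.2 uses similar by-phase wording for the acute-phase reactants. For hematology and chemistry, the by-visit tables LB001SP and LB004SP stop at Month 18. The CTCAE shift tables (LB005SP onward) use all post-baseline data but do not single out extended follow-up. No visible output specifies an extended follow-up change for those tests.

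**The case against.** The strongest reply is that little is lost. Changes through closeout keep the pre-rituximab baseline, and levels are summarized at each visit. In the illustration a reader would see 10, 7.0 and 7.75 g/L, with −3.0 reported at closeout. A reader might infer that the plan conceals the fall in IgG. The documents do not support that: one derived statistic in one phase is affected, and its definition is stated openly.

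A reader might also infer that IgG must be low at phase start because these patients are depleted. Depletion here refers to peripheral B cells. Nothing in the documents shows that immunoglobulins, hematology or chemistry are low at that point, and if they are not, the two baselines nearly agree.

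A third inference is that the phase exists to show immunoglobulin recovery. Protocol 3.1.4 and SAP 1 tie it to B-cell counts. SAP 2 and protocol 3.1.3 still mention immunoglobulins, and those passages need reconciling, but they do not establish such a purpose.

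Finally, change from phase start answers a fair question about what happened after closeout. The pre-rituximab value is also not a clean normal: patients have severe active disease, receive intravenous steroids beforehand, and may have had earlier immunosuppression.

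All of this stands as a limit on the consequence. It supports keeping change from phase start as an additional measure. It does not explain why the only change reported in this phase should use a different reference from the other two, and it does not repair the exclusion sentence or the data-set definition.

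**Conclusion.** The point holds in limited form. Under SAP 3.2.3, immunoglobulin changes in extended follow-up omit Y0 − Yc and are not comparable with induction or follow-up changes. The size is unknown from the documents: zero if nothing was lost before closeout, and 0.8 to 6.0 g/L across the assumed IgG range.

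The conclusion rests on the phase-start value being post-rituximab, which the schedule makes normal, and on SAP 7.3 being applied to this phase as written. Part of the PD section is redacted, so an immunoglobulin display there cannot be checked. The general rule reaches hematology and chemistry too, but the claim that reported results for them are distorted has no visible output behind it.

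The study tests no hypotheses, and only patients still depleted at closeout enter this phase, so this is an inexpensive improvement in reporting and does not threaten the primary analysis. The internal mismatches in 3.2.3 and 2.3.3 need correcting whichever baseline is preferred.

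**What to change.** - **SAP 3.2.3:** extend the CD19 exception. Report change from the 3.2.1 pre-rituximab baseline for immunoglobulins, and for any other laboratory change summarized in extended follow-up.
- **Display:** keep change from phase start as a second column, labelled as such.
- **Exclusion sentence:** apply it separately to each column, so that a patient is left out only where the baseline for that column is missing.
- **SAP 2.3.3:** state that the data set includes all pre-rituximab values, including Day 1 pre-dose, and the phase-start value.

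The cost is one new sentence, two aligned sentences and one extra column. No new data are needed: SAP Appendix 2 already schedules immunoglobulins, hematology and chemistry at screening and baseline.

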3.3 Visit Windows

For summarization by time-point data will be assigned to an analysis visit based on the date of the assessment relative to the date of study treatment Day 1 (treatment start). The visit assessment windows given in Table 1 will be used to assign data to planned study assessments:

Table 1 Analysis Visit Time-point Windows

Assessment Month	Planned Treatment Day ⁽¹⁾	Day Number ⁽¹⁾ Range
Baseline	1	Day 1
Week 1	8	Days 5 – 11
Week 2	15	Days 12 – 18
Week 3	22	Days 19 – 25
Month 1	29	Days 26 – 44
Month 2	60	Days 45 – 75
Month 4	120	Days 105 – 135
Month 6	180	Days 165 – 210
Month 9	270	Days 240 – 300
Month 12	365	Days 335 – 395
Month 15	455	Days 425 – 485
Month 18	545	Days 500 – 590
Month 21 or Follow-up month 3	**	Planned Treatment Day ± 45 days
Month 24 or Follow-up month 6	**	Planned Treatment Day ± 45 days
...

** Planned Treatment Day = Month 18 Planned Treatment Day + 92 × (number of follow-up month /3)

Assessments made outside of these assessment windows will be listed but not used in *by time-point* summaries.

⁽¹⁾ For each patient, the day of the baseline visit will be defined as treatment day 1 and subsequent time-points will be assigned a treatment day calculated as:
(date of assessment – date of baseline) + 1

For a given measurement and analysis visit the following rules will be used to decide which value to use in the analysis:

- Protocol defined visit assessments will take priority over unscheduled visit data; that is, unscheduled visit data will only be used if there is no scheduled visit results within the same time window.
- If more than one assessment falls within the same window, then use the measurement taken nearest to the planned day. In the case of a tie, use the earlier measurement.
- Assessments made outside of these analysis visit windows will be listed but not used in by time-point summaries.

3.4 Analysis Overview

Safety Analyses

All safety analyses will be done on safety population and by study phase.

Abnormal electrocardiogram (ECG), chest X-ray and chest CT scan findings are to be reported.

Details of the analyses and outputs are given in Section [5](#) to [9](#).

Efficacy Analysis

[REDACTED]

[REDACTED]

Pharmacodynamic Analyses

[REDACTED]

Subgroup Analyses

The sample size for this study is too small to permit subgroup analyses.

4. BASELINE DEMOGRAPHICS AND BASELINE INFORMATION

Descriptive summaries of the following information will be produced to characterize baseline characteristics for the safety population:

- Demographic characteristics, including:
 - age, both as descriptive summary and as counts and percentages falling into the following categories:
 - 2 – 11 years
 - 12 – 17 years
 - sex
 - race
 - ethnicity
 - height
 - weight
 - body surface area
- Baseline disease characteristics:
 - GPA or MPA disease
 - ANCA result (C-ANCA, P-ANCA, Negative)
 - Duration of disease
 - Pediatric Vasculitis Damage Index (PVDI)
- Previous and current treatment for GPA or MPA
 - A glossary showing the mapping of investigator verbatim terms to coded medications will be produced also
- Immunization history
- Patients' medical history, grouped by preferred term within SOC
 - A glossary showing the mapping of investigator verbatim terms to coded diseases will be produced also
- Alcohol, tobacco and substance use
- Female reproductive status

4.1 Analysis of Study Conduct

The following data will be summarized for the safety population, giving the number and percentage of patients who:

- Had major protocol deviations occurring during the remission induction phase
- Were withdrawn prematurely from the study
- Entered extended follow-up (To be added later as CSR addendum)
- Entered extended follow-up
- Switched to local standard care during the study by study phase

In addition, summaries will be provided of:

- Non-study treatments given for GPA and MPA by study phase
- Concomitant medications received by study phase

4.2 Analysis Populations and Disposition

The following summaries will be produced:

- Analysis populations
- Patient disposition by study phase (remission induction phase, follow-up phase, extended follow-up phase)

4.3 Baseline Output Specifications

ID: DS101SP	STREAM Template: APT01
Analysis Populations	Analysis Population: Treated Patients (Assigned Treatment)
	Analysis Variables: Number of patients for the only analysis population, as shown in the mockup.
	Numeric Precision and Formatting of Statistics: Use mockup.

Analysis Population	Rituximab
Treated Patients AASL.RP (Assigned Treatment AASL.ARM)	nn
Safety Evaluable Population ASL.SE (Treatment Received AASL.ACTARM)	nn (xx.x%)
Population (Safety population with at least one evaluable PK sample)	nn (xx.x%)

ID: DS001SP
 
Enrolment by Region, Country, and Investigator Number and Name
	
STREAM Template: ENT02
 
Analysis Population: Samedical history fety Evaluable Population
 
Analysis Variables: Group centers by region and country.
 
Sort order: Alphabetical by region, and then by decreasing total number of patients treated. Percentages are based on N.
 
Numeric Precision and Formatting of Statistics: Use standard display in the mockup.

--	---

Region ASL.GEOREGC1	Country ASL.COUNTRY , Investigator Number ASL.INVID / Name ASL.INVNAM	Rituximab (N=nnn)
Region 1		nn (xx.x%)
Country 1		nn (xx.x%)
9318 / Name 1		nn (xx.x%)
11518 / Name 2		nn (xx.x%)
...		nn (xx.x%)
Country 2		nn (xx.x%)
88431 / Name 1		nn (xx.x%)
8876 / Name 2		nn (xx.x%)
...		nn (xx.x%)
Region 2		nn (xx.x%)
Country 1		nn (xx.x%)
77649 / Name 1		nn (xx.x%)
...		nn (xx.x%)

ID: DM001SP
 
Demographic and Baseline Characteristics
	
STREAM Template: DMT01
 
Analysis Population: Safety Evaluable Population
 
Analysis Variables: See mockup.
 
Statistics and Calculation Methods: For each variable, summary statistics are based on the number of patients in the corresponding “n” row.
 
Number of concomitant diseases started before or at baseline and continued after.
 
Numeric Precision and Formatting of Statistics: Use standard display in the mockup.

--	--

	Rituximab (N=nnn)
Age (yr) ASL.AGE	
n	nnn
Mean (SD)	xx.x (xx.x)
Median	xx.x
Q1 – Q3 (IQR)	xx.x – xx.x (xx.x)
Min–Max	xx–xx
Age group (yr) ASL.AGEG	
n	nnn
2 to 11	nn (xx.x%)
12 to 17	nn (xx.x%)
Sex ASL.SEX	
n	nnn
Male	nn (xx.x%)
Female	nn (xx.x%)
Ethnicity ASL.ETHNIC	
n	nnn
Hispanic or Latino	nn (xx.x%)
Not Hispanic or Latino	nn (xx.x%)
Not Reported	nn (xx.x%)
Unknown	nn (xx.x%)
Race ASL.RACE	
n	nnn
American Indian or Alaska Native	nn (xx.x%)
Asian	nn (xx.x%)
Black or African American	nn (xx.x%)
Native Hawaiian or other Pacific Islander	nn (xx.x%)
White	nn (xx.x%)
Multiple	nn (xx.x%)
Other	nn (xx.x%)
Unknown	nn (xx.x%)
Height (cm) ASL.BWT	
n	nnn
Mean (SD)	xx.x (xx.x)
Median	xx.x
Q1 – Q3 (IQR)	xx.x – xx.x (xx.x)
Min–Max	xx–xx

	Rituximab (N=nnn)
Weight (kg) ASL.BWT	
n	nn
Mean (SD)	xx.x (xx.x)
Median	xx.x
Q1 – Q3 (IQR)	xx.x – xx.x (xx.x)
Min–Max	xx–xx
Body-mass index (kg/m2) ASL.BBMI	
n	nn
Mean (SD)	xx.x (xx.x)
Median	xx.x
Q1 – Q3 (IQR)	xx.x – xx.x (xx.x)
Min–Max	xx–xx
Concomitant Diseases (continuing at Baseline)	
n	nn
No concomitant diseases	nn (xx.x%)
1 concomitant disease	nn (xx.x%)
2 concomitant diseases	nn (xx.x%)
>=3 concomitant diseases	nn (xx.x%)
Smoking history	
n	nn
Current	nn (xx.x%)
Previous	nn (xx.x%)
Never	nn (xx.x%)
Alcohol history	
n	nn
Current	nn (xx.x%)
Previous	nn (xx.x%)
Never	nn (xx.x%)

Estimated GFR (Schwartz formula) (mL/min/1.73 m2)	
n	nn
Mean (SD)	xx.x (xx.x)
Median	xx.x
Q1 – Q3 (IQR)	xx.x – xx.x (xx.x)
Min–Max	xx.x–xx.x
immunofluorescence (IF) ANCA status	
Negative	nn (xx.x%)
cANCA	nn (xx.x%)
pANCA	nn (xx.x%)
MPO	nn (xx.x%)
PR3	nn (xx.x%)
BVAS/WG Score	
n	nn
Mean (SD)	xx.x (xx.x)
Median	xx.x
Q1 – Q3 (IQR)	xx.x – xx.x (xx.x)
Min–Max	xx.x–xx.x

Current Disease Status

n	
Severe Flare/New Disease	nn (xx.x%)
Limited Flare/New Disease	nn (xx.x%)
Persistent Severe Disease	nn (xx.x%)
Persistent Limited Disease	nn (xx.x%)
Remission	nn (xx.x%)

BVAS/WG PGA

n	nn
Mean (SD)	xx.x (xx.x)
Median	xx.x
Q1 – Q3 (IQR)	xx.x – xx.x (xx.x)
Min–Max	xx.x–xx.x

PVAS Score

n	nn
Mean (SD)	xx.x (xx.x)
Median	xx.x
Q1 – Q3 (IQR)	xx.x – xx.x (xx.x)
Min–Max	xx.x–xx.x

PVDI Score

n	nn
Mean (SD)	xx.x (xx.x)
Median	xx.x
Q1 – Q3 (IQR)	xx.x – xx.x (xx.x)
Min–Max	xx.x–xx.x

[figure not shown]
PVDI Average School Absence (days)

[figure not shown]
n	nn
=<1	nn (xx.x%)
>1 - 4	nn (xx.x%)
>4 - 10	nn (xx.x%)
>10	nn (xx.x%)


ID: DM002SP
 
GPA / MPA History
	
STREAM Template: DMT01
 
Analysis Population: Safety Evaluable Population
 
Analysis Variables: See mockup.
 
Statistics and Calculation Methods: For each variable, summary statistics are based on the number of patients in the corresponding “n” row.
 
Major Renal Disease is taken from eCRF page, BVAS/ WG and PGA. If both hematuria and RBC casts are present, score only the RBC casts.
 
Summaries are based on Medical history and Concomitant medication domains, and Screening records for other assessments.
 
Most severe "Current Disease Status" is used for summary if patient has multiple disease status from Screening.
 
Disease duration is from the start date of disease to start of study drug at baseline.
 
Numeric Precision and Formatting of Statistics: See mockup.

---	--

	Rituximab (N=nnn)
Diagnosis	
n	nn
GPA Newly diagnosed	nn (xx.x%)
MPA Newly diagnosed	nn (xx.x%)
GPA relapsed	nn (xx.x%)
MPA relapsed	nn (xx.x%)
Disease duration (months)	
n	nn
Mean (SD)	xx.x (xx.x)
Median	xx.x
Q1 – Q3 (IQR)	xx.x – xx.x (xx.x)
Min–Max	xx–xx
Prior CYC therapy	
n	nn
Yes	nn (xx.x%)
No	nn (xx.x%)
Major Renal Disease*	
n	nn
Yes	nn (xx.x%)
No	nn (xx.x%)

* Major Renal Disease is taken from eCRF page, BVAS/ WG and PGA. If both hematuria and RBC casts are present, score only the RBC casts (the major item)

ID: DM003SP Listing of Patients who Discontinued from Study	STREAM Template: DSL02 Analysis Population: Safety Evaluable Population Variables Displayed: Add a columns for “date of study discontinuation” and “study phase” to DSL02
--	--

ID: DS201SP Patient Disposition	STREAM Template: DST01 Analysis Population: Safety Evaluable Population Analysis Variables: See mockup.
--	--

Study	Rituximab (N = 25)
Completed 6 Month Remission Induction Phase	nn (xx.xx%)
Completed 18 Months on study	nn (xx.xx%)
Completed study from baseline to common-closeout*	nn (xx.xx%)
Entered extended safety follow-up+	nn (xx.xx%)
Discontinued Study	nn (xx.xx%)
Reason 1	nn (xx.xx%)
Reason 2	nn (xx.xx%)
Reason 3	nn (xx.xx%)
...	

*The common closeout date (10May2018) occurred 18 months after the enrollment of the last patient.
 +patients whose B cells remain depleted below LLN for the population entered extended safety follow up.

ID: DS002SP	STREAM Template: DST01
Patients Discontinued from Study Treatment	Analysis Population: Safety Evaluable Population
	Analysis Variables: See mockup

Status	Rituximab (N=25)
Completed Planned RTX Treatment	nn (xx.x%)
Discontinued Treatment During Study	nn (xx.x%)
Lost To Follow-Up	nn (xx.x%)
Patient Is Transitioning To Adult Care.	nn (xx.x%)
Transfer To Adult Services	nn (xx.x%)
Transferred To Adult Services And Unable To Stay In Follow Up Of Pi	nn (xx.x%)
Transferred To Adult Site	nn (xx.x%)
Transferring To Adult Services	nn (xx.x%)
Withdrawal By Subject	nn (xx.x%)

ID: CM001SP	STREAM Template: None
Listing of Concomitant Diseases other than MPA/GPA	Analysis Population: Safety Evaluable Population
	Variables Displayed: See mockup.
	Concomitant Disease is defined as a disease started on or before baseline and continued after.
	Exclude MPA/GPA diseases from the listing.

Center/Patient ID - Age/Sex/Race Concurrent Disease MedDRA Preferred Term	Date of First Study Drug Administration	Start Date of Disease / Study Day of onset	Duration in Days	Outcome
██████████ ANEAMIA NOS	██████████	██████████ / -60	1	Resolved
██████████ APPETITE DECREASED	██████████	██████████ / -91	2	Resolved
██████████ DIARRHEA NOS	██████████	██████████ / -425	2	Resolved

ID: CM002SP
 
Listing of Previous Medications for GPA/MPA
	
STREAM Template: None
 
Analysis Population: Safety Evaluable Population
 
Variables Displayed: Include medications started and ended on or before baseline.
 
See mockup.

--	---

Center/Patient ID - Age/Sex/Race Standardized Medication Name Reported Name of Drug, Medication or Therapy	Dose (unit)	Date of First Study Drug Administration	Start Date of Previous Medication / Study Day	Stop Date of Previous Medication / Study Day
██████████ ANEAMIA NOS	xx	██████████	██████████ / -34	██████████ / -34
APPETITE DECREASED	xx	██████████	██████████ / -122	██████████ / -122
██████████ DIARRHEA NOS	xx	██████████	██████████ / -78	██████████ / -78

ID: CM003SP
 
Listing of Concomitant Medications for GPA/MPA
	
STREAM Template: None
 
Analysis Population: Safety Evaluable Population
 
Variables Displayed: Include medications started anytime (after, on or before baseline) and is ongoing during study.
 
See mockup.

---	--

Center/Patient ID - Age/Sex/Race Standardized Medication Name Reported Name of Drug, Medication or Therapy	Dose (unit)	Date of First Study Drug Administration	Start Date of Concomitant Medication / Study Day	Stop Date of Concomitant Medication / Study Day
██████████ ANEAMIA NOS	xx	██████████	██████████ / -34	██████████ -34
APPETITE DECREASED	xx	██████████	██████████ / -122	██████████ / -122
██████████ DIARRHEA NOS	xx	██████████	██████████ / -78	██████████ / -78

ID: CM003.1SP
 
Listing of Concomitant Medications for GPA/MPA Ongoing at Baseline
	
STREAM Template: None
 
Analysis Population: Safety Evaluable Population
 
Variables Displayed: Include medications started on or before baseline and is ongoing at baseline.
 
See mockup CM003SP.

---	--

ID: CM003.2SP
 
Listing of Concomitant Medications for non GPA/MPA Indications
	
STREAM Template: None
 
Analysis Population: Safety Evaluable Population
 
Variables Displayed: Include medications started anytime (after, on or before baseline) and is ongoing during study for non MPA/GPA indications.
 
Exclude vaccines from the con meds if the start date is before day 1.
 
See mockup for CM003SP.

---	---

ID: MH001SP
 
Immunization History
	
STREAM Template: DMT01
 
Analysis Population: Safety Evaluable Population
 
Analysis Variables: See mockup.
 
Statistics and Calculation Methods: For each variable, summary statistics are based on the number of patients in the corresponding “n” row.
 
Numeric Precision and Formatting of Statistics: See mockup

---	--

	Rituximab (N=nnn)
Tetanus Immunoglobulin	
n	nn
Yes	nn (xx.x%)
No	nn (xx.x%)
Hepatitis B Immunoglobulin	
n	nn
Yes	nn (xx.x%)
No	nn (xx.x%)
Hepatitis A Immunoglobulin	
n	nn
Yes	nn (xx.x%)
No	nn (xx.x%)
Rabies Antiserum	
n	nn
Yes	nn (xx.x%)
No	nn (xx.x%)
Varicella Zoster Immunoglobulin	
n	nn
Yes	nn (xx.x%)
No	nn (xx.x%)
Other Immunoglobulin	
n	nn
Yes	nn (xx.x%)
No	nn (xx.x%)

ID: MH001_1SP	STREAM Template: DMT01
Vaccination History	Analysis Population: Safety Evaluable Population
	Analysis Variables: See mockup.
	Statistics and Calculation Methods: For each variable, summary statistics are based on the number of patients in the corresponding "n" row.
	Use CMCAT = "VACCITINATOIN" and CMOCCUR="Y".
	Numeric Precision and Formatting of Statistics: See mockup

	Rituximab (N=nnn)
Tetanus Immunoglobulin	nn (xx.x%)
Hepatitis B Immunoglobulin	nn (xx.x%)
Hepatitis A Immunoglobulin	nn (xx.x%)
Rabies Antiserum	nn (xx.x%)

